SECTION Q: CANCER BEHAVIOR INVENTORY (MERLUZZI)—Survivors

NOTE: We will adapt the following items based on experiences of Nueva Vida and [name] in administering these items to Latina survivors

The next questions are about things you might do when receiving treatment for cancer. On a scale of 1 to 9, 1 meaning “not at all confident” and 9 meaning “totally confident, please tell me how confident you are that you can accomplish each behavior.

	Not at all confident				Moderately confident				Totally confident
Maintaining independence.	 1	 2	 3	 4	 5	 6	 7	 8	 9
Maintaining a positive attitude.	 1	 2	 3	 4	 5	 6	 7	 8	 9
Accepting that I have cancer.	 1	 2	 3	 4	 5	 6	 7	 8	 9
Maintaining work activity.	 1	 2	 3	 4	 5	 6	 7	 8	 9
Asking nurses questions.	 1	 2	 3	 4	 5	 6	 7	 8	 9
Remaining relaxed throughout treatments and not allowing scary thoughts.	 1	 2	 3	 4	 5	 6	 7	 8	 9
Seeking support from people & groups outside the family.	 1	 2	 3	 4	 5	 6	 7	 8	 9
Maintaining a daily routine.	 1	 2	 3	 4	 5	 6	 7	 8	 9
Asking technologists questions.	 1	 2	 3	 4	 5	 6	 7	 8	 9
Using denial. (Putting things out of my mind at times)	 1	 2	 3	 4	 5	 6	 7	 8	 9
Remaining relaxed throughout treatment (chemotherapy, radiation).	 1	 2	 3	 4	 5	 6	 7	 8	 9
Coping with physical changes.	 1	 2	 3	 4	 5	 6	 7	 8	 9
Ignoring things that cannot be death with.	 1	 2	 3	 4	 5	 6	 7	 8	 9
Actively participating in treatment decisions.	 1	 2	 3	 4	 5	 6	 7	 8	 9
Sharing feelings of concern..	 1	 2	 3	 4	 5	 6	 7	 8	 9
Remaining relaxed while waiting at least one hour for my appointment.	 1	 2	 3	 4	 5	 6	 7	 8	 9
Expressing personal feelings of anger or hostility.	 1	 2	 3	 4	 5	 6	 7	 8	 9
Keeping busy with activities.	 1	 2	 3	 4	 5	 6	 7	 8	 9
Finding an escape (“getting away from it all” at times).	 1	 2	 3	 4	 5	 6	 7	 8	 9
Reducing any anxiety with getting my blood drawn.	 1	 2	 3	 4	 5	 6	 7	 8	 9

PRINCIPAL INVESTIGATOR (LAST, FIRST, MIDDLE): [name]

	Not at all confident				Moderately confident				Totally confident
Maintaining a sense of humor.	 1	 2	 3	 4	 5	 6	 7	 8	 9
Accepting physical changes or limitations caused by cancer treatment.	 1	 2	 3	 4	 5	 6	 7	 8	 9
Seeking consolation.	 1	 2	 3	 4	 5	 6	 7	 8	 9
Reducing any nausea associated with treatment (chemotherapy, radiation).	 1	 2	 3	 4	 5	 6	 7	 8	 9
Maintaining hope.	 1	 2	 3	 4	 5	 6	 7	 8	 9
Asking physicians questions.	 1	 2	 3	 4	 5	 6	 7	 8	 9
Doing something, anything.	 1	 2	 3	 4	 5	 6	 7	 8	 9
Managing pain.	 1	 2	 3	 4	 5	 6	 7	 8	 9
Managing nausea and vomiting.	 1	 2	 3	 4	 5	 6	 7	 8	 9
Controlling my negative feelings about cancer.	 1	 2	 3	 4	 5	 6	 7	 8	 9

SECTION R: FAMILISM SCALE – Survivors and Caregivers

The following questions pertain to your perception of family support. Using the scale below, we would like for you to answer to the next statements on a scale of 1 to 10, where 1 is strongly disagree and 10 strongly agree.

	Strongly disagree									Strongly agree
A person should always live near his or her parents and spend time with them on a regular basis.	1	2	3	4	5	6	7	8	9	10
A person should always support members of the extended family, for example, aunts, uncles, and in-laws, if they are in need even it is a big sacrifice.	1	2	3	4	5	6	7	8	9	10
A person should rely on his or her family if the need arises	1	2	3	4	5	6	7	8	9	10
A person should often do activities with his or her immediate and extended families, for example, eat meals, play games, or go somewhere together.	1	2	3	4	5	6	7	8	9	10
A person should help his or her elderly parents in times of need, for example, helping financially or sharing a house.	1	2	3	4	5	6	7	8	9	10

PRINCIPAL INVESTIGATOR (LAST, FIRST, MIDDLE): [name]

SECTION 5: CAREGIVER INVENTORY –Caregivers Only

The next questions are about things you might do when caring for a person with an illness. We are interested in how confident you are that you can do those things. Make sure your ratings reflect your confidence whether or not you have done these in the past. So, your rating should reflect your confidence that you could do these things in the future.. On a scale of 1 to 9, 1 meaning “not at all confident” and 9 meaning “totally confident, please tell me how confident you are that you can accomplish each behavior.

	Not at all confident				Moderately confident				Totally confident
Coping with information overload.	 1	 2	 3	 4	 5	 6	 7	 8	 9
Listening and learning from the person as to how to care better for her.	 1	 2	 3	 4	 5	 6	 7	 8	 9
Letting go of things I can't control.	 1	 2	 3	 4	 5	 6	 7	 8	 9
Expressing negative feelings about the illness.	 1	 2	 3	 4	 5	 6	 7	 8	 9
Maintaining hope.	 1	 2	 3	 4	 5	 6	 7	 8	 9
Being able to notice the “good moments” in caregiving when they occur.	 1	 2	 3	 4	 5	 6	 7	 8	 9
Allowing the person to have and express her own feelings.	 1	 2	 3	 4	 5	 6	 7	 8	 9
Assisting the person with activities, such as feeding, washing, dressing or using the toilet.	 1	 2	 3	 4	 5	 6	 7	 8	 9
Continuing to take care of yourself (for example: exercise, diet, sleep).	 1	 2	 3	 4	 5	 6	 7	 8	 9
Talking openly and honestly with the person.	 1	 2	 3	 4	 5	 6	 7	 8	 9
Continuing to engage in personal activities that you like to do.	 1	 2	 3	 4	 5	 6	 7	 8	 9
Talking about death and dying.	 1	 2	 3	 4	 5	 6	 7	 8	 9
Providing emotional support to the person I'm caring for.	 1	 2	 3	 4	 5	 6	 7	 8	 9
Understanding medical information from doctors, nurses or other sources.	 1	 2	 3	 4	 5	 6	 7	 8	 9
Seeking support for yourself.	 1	 2	 3	 4	 5	 6	 7	 8	 9
Dealing with feelings of helplessness.	 1	 2	 3	 4	 5	 6	 7	 8	 9
Dealing with the person expressing negative feelings toward you when they occur.	 1	 2	 3	 4	 5	 6	 7	 8	 9
Assisting and encouraging the person in following through with all treatments and taking all prescribed medications.	 1	 2	 3	 4	 5	 6	 7	 8	 9

PRINCIPAL INVESTIGATOR (LAST, FIRST, MIDDLE): [name]

	Not at all confident				Moderately confident				Totally confident
Asking physicians and nurses questions.	 1	 2	 3	 4	 5	 6	 7	 8	 9
Dealing with criticism from others.	 1	 2	 3	 4	 5	 6	 7	 8	 9
Maintaining a close relationship with the person I'm caring for. .	 1	 2	 3	 4	 5	 6	 7	 8	 9

SECTION T: DEMOGRAPHICS

This is the last section. We have some questions about you. You can skip any question you do not wish to answer; however this information is important for our study.

What is your birth date? ____ / ____ / ____ (MM/DD/YY)

Which is your ethnicity? Please choose one answer.

Hispanic/Latino	1
Non-Hispanic/Latino	2

What is your race? I will read a list and please tell me which one best describes you.

	Check below
Black or African American	
White or Caucasian	
American Indian/Alaska Native	
Asian	
Native Hawaiian or other Pacific Islander	
More than One Race	
Don't Know/Unsure	
Prefer Not to Answer	

What is the highest grade or level of schooling you have completed? Have you completed...

	Check below		Check below
No formal schooling		11 th grade	
1 st grade		12 th grade	
2 nd grade		College 1 year	
3 rd grade		College 2 years	
4 th grade		College 3 years	
5 th grade		College 4 years	
6 th grade		College 5 years	
7 th grade		College 6 years	
8 th grade		Training after high school	
9 th grade		Other. Specify: _____	
10 th grade			

PRINCIPAL INVESTIGATOR (LAST, FIRST, MIDDLE): [name]

Where or in which country were you born? Were you born in....

	Check Below		Check Below
Argentina		México	
Bolivia		Nicaragua	
Brasil		Perú	
Colombia		Puerto Rico	
Chile		Republica Dominicana	
Ecuador		United States. Which generation you are (first, second, third?) Specify: _____	
El Salvador		Other (specify) _____	
Guatemala			

How many years have you lived in the United States? _____

What is your current work status? Please select one. Are you...

- Working part time
- Working full time
- Full- or part-time student
- Retired
- Never worked
- Unemployed/looking for work
- Receiving disability

What is your average yearly household income (combined income of everyone living in your house)? Please choose the response that fits best.

- | | | |
|--|---|-------------------------------------|
|  Less than \$9,999 |  \$60,000-\$69,999 |  Don't know |
|  \$10,000-\$19,999 |  \$70,000-\$79,999 | |
|  \$20,000-\$29,999 |  \$80,000-\$89,999 | |
|  \$30,000-\$39,999 |  \$90,000-\$99,999 | |
|  \$40,000-\$49,999 |  More than \$100,000 | |
|  \$50,000-\$59,999 |  Prefer not to answer | |

What is your current marital status? (Select one)

- Single
- Separated
- Divorced
- Widowed
- Married
- Living with a partner

Do you have a doctor (primary care, family doctor) that you see regularly (routine check-ups, treatment of colds or minor health concerns)? ___ Yes ___ No

Are you currently covered by health insurance? ___ Yes ___ No

If no, skip next question.

PRINCIPAL INVESTIGATOR (LAST, FIRST, MIDDLE): [name]

What type of health insurance do you have?

- Group insurance (through my work or my partner's work)
- Government insurance (Medicare, Medicaid)
- Military insurance Private insurance
- Not applicable; I do not currently have health insurance

Have you ever been denied health insurance for any reason?

- Yes
- No

If yes, why were you denied insurance?

Is there any other thing that we hadn't asked you that you want to share with us about what impacts our quality of life and your general wellness as a breast cancer survivor or caregiver?

May we contact you in the future for other research studies? You would be free to participate or decline at that time.

- Yes, you may contact me about future research
- No, I prefer not to be contacted about future research

If Yes: Can you give us other additional telephone numbers or an email address where we can contact you? Please note this information will not be connected with your study data.

To thank you for your time, please indicate which gift card you would like to receive:

- Target Stores
- Safeway Foods (or other local grocery store)
- Amazon.com

NOTE: These stores may change based on feedback from the team.

These are all the questions that we had for you today. Thank you for taking the time to participate in this study. We hope that this will help other survivors and caregivers in the future.

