is also designed to alleviate distress in terms of normalizing the experiences of or difficulties with coping as a survivor or caregiver, providing support, giving positive feedback and modeling acceptance.⁵¹ Distress is changed through cognitive restructuring.⁵² We hypothesize that changes in QOL will be due to improved communication self-efficacy, improved social support and decreased distress in PCI vs. UC participants.

Choice of Outcomes. We selected outcomes that are patient-centered, clinically meaningful and relevant to stakeholder decision-makers. Foremost, our primary outcome variable is QOL, an outcome valuable to Latina survivors,¹⁵ caregivers,³⁴ clinicians, service-providers and stakeholders (see Letters of Support). Secondary outcomes include communication (survivor-caregiver and survivor-provider), satisfaction with cancer care and adherence to guideline concurrent follow-up care. Most of the instruments we will use are validated in Spanish. For scales not previously translated/tested in Spanish, we will follow procedures of [name], who has expertise in the translation and cultural adaptation of survey instruments. Missing data will be minimized as trained, bilingual and bicultural research personnel will administer assessments by telephone. Of note, study assessments will be completed by GUMC research personnel not associated with the delivery of the intervention. We will make every effort to blind the assessor to the participants' randomization assignment.

Background Factors. (a) **Sociodemographics** include sex, age, marital and insurance status, race, education, income. (b) **Medical history** includes history of co-morbidities in both the survivor and the caregiver. We will also assess whether participants (survivor or caregiver) have provided care to another ill person.

Cultural Factors. (a) **Breast cancer stigma** will be measured using eight 5-point Likert scale items from the stigma subscale of the Body Image after Breast Cancer Questionnaire.⁹⁴ We have translated this subscale into Spanish ($\alpha=0.83$).² (b) We will measure **religious coping** with the Religious Coping Scale.⁹⁵ (c) **Familismo** will be assessed with the 5-item Familism Scale.⁹⁶ Items are rated on a 10-point Likert scale and capture concepts such as family support and familial interconnectedness. (d) **Acculturation** will be measured with the Short-Acculturation Scale⁹⁷ including language use, media preferences and ethnic social relations ($\alpha=.90$).²

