Secondary Outcomes. (a) **Communication with Providers** will be measured with a validated 15-item measure.¹⁰⁸ Participants rate providers from poor to excellent with a sample item as "Treated me with respect." Communication with caregivers will be measured through several dyadic-based measures. (b) **Satisfaction with care** will be measured with 3 reliable items used by [name] in her prior work.¹⁰⁹ Finally, (c) **Adherence to guideline-concurrent follow-up care** will be based on following care guidelines of the American Society of Clinical Oncology¹¹⁰ and measured using self-report items as done in prior work.¹¹¹

Dyadic Factors. (a) **Dyadic support** will be measured with the 5-item scale by Northouse^{112,113} which assesses the perceived support received by each member of the patient-caregiver dyad. (b) **Dyadic perspective**, meaning considering another's point of view about a specific topic like breast cancer, will be assessed with a modified version of the Thinking Beyond Oneself scale.¹¹⁴ This scale has been used in dyadic cancer control research.⁶³ (c) **Social constraints** will be measured with the 5-item Social Constraints Scale.^{115,116} We have used a Spanish translation of this scale and obtained good internal consistency.²

Process Variables. (a) **Satisfaction.** We will assess satisfaction with PCI and UC. (b) **Intervention fidelity.** We will measure adherence to intervention protocols, participants' engagement (attendance, participation), exposure to intervention content, quality of intervention delivery and differentiation between PCI and UC arms.^{117,118} Staff will complete session contact logs and evaluation forms.¹¹⁸

C.2. Analytic Methods

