Study Population. Inclusion/Exclusion Criteria. Latina breast cancer survivors will be eligible for this study if they: 1) self-identify as Latina, 2) speak English or Spanish and 3) can identify at least one primary, adult caregiver. Caregivers of Latina breast cancer survivors will be eligible if they are aged 21 to 80 years old and speak English or Spanish. Caregivers can be any adult identified by the survivor as providing care (e.g., spouse, adult child, friend). If a survivor has more than one primary caregiver, only one will be recruited to participate. We will recruit participants from our four sites. Area hospitals (St. Luke's Hospital; Doctors Community Hospital) with diverse Latino populations will refer eligible participants. Exclusion criteria are (a) inability to understand spoken English and/or Spanish or (b) cognitive impairment that precludes informed consent (determined by the PIs or Co-Investigators who are mental health professionals). We expect the survivors who enroll in the study to be similar to the survivors who are eligible for services across the four

PRINCIPAL INVESTIGATOR (LAST, FIRST, MIDDLE): [name]

community partner sites As such, ***we anticipate that our findings will be generalizable to the 8,000+ Latino families who receive care/support through our community partners.***

Anticipated Accrual. Our four sites collectively see about 300 newly diagnosed Latina breast cancer survivors each year (Table 5). From our prior recruitment efforts of Latinas, we conservatively estimate a minimum of 40% per year (n=125) will be eligible for the present study.

Table 5. Estimated Number of People Served.	Nueva Vida, Inc.	Latinas Contra Cancer	SHARE/ Latina Share	Gilda's Club NYC	Totals
Annual # of cancer survivors or family members served ^a	4,000	1,000	6,000	7,300	18,300
Annual # of Latino survivors or family members served ^a	4,000	1,000	2,000	1,200	8,200
Annual # Latina breast cancer survivors served	230	70	215	300	815
Annual # newly diagnosed Latina breast cancer survivors	70	50	80	100	300
Estimated Distribution of Countries-of-Origin among Latinos served	DC Site	CA Site	NY Sites		Estimated Study Distribution
% South American	27%	10%	11%		14%
% Central American ^b	57%	1%	5%		18%
%Dominican Republic	1%	1%	15%		8%
% Puerto Rican	1%	8%	21%		12%
% Caribbean / Other	6%	7%	9%		8%
% Mexican	6%	68%	27%		32%
% United States	2%	5%	11%		8%

^aThrough in-person, print or online support or educational programs.

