What language(s) do you usually speak at home?	1	2	3	4	5	6
In which language(s) do you usually think?	1	2	3	4	5	6
What language(s) do you usually speak with your friends?	1	2	3	4	5	6
In what language(s) are the T.V. and Radio programs you usually watch?	1	2	3	4	5	6

The next questions are about your friends. Please circle your answer.

	All Latinos/Hispanics	More Latinos than Americans	About Half & Half	More Americans than Latinos	All Americans	Other?
Your closest friends are	1	2	3	4	5	6
You prefer going to social gatherings/parties at which the people are	1	2	3	4	5	6
If you could choose your children's friends you would want them to be	1	2	3	4	5	6

PRINCIPAL INVESTIGATOR (LAST, FIRST, MIDDLE): [name]

SECTION E: SOCIAL SUPPORT – Survivors and Caregivers

I will read a list of things that other people do for us or give us that may be helpful or supportive. Please listen to each statement carefully and indicate an answer that is closest to your situation. Answering “1” would mean that you get that type of support “much less than you would like” and answering “5” would mean that you get that type of support “as much as you would like.” Answer each item as best as you can. There are no rights or wrong answers.

	Much less than I would like					As much as I would like
	1	2	3	4	5	
I have people who care about what happens to me.	1	2	3	4	5	
I get love and affection.	1	2	3	4	5	
I get chances to talk to someone about problems at work or with my homework.	1	2	3	4	5	
I get chances to talk to someone I trust about my personal and family problems.	1	2	3	4	5	
I get chances to talk about money matters.	1	2	3	4	5	
I get invitations to go out and do things with other people.	1	2	3	4	5	
I get useful advice about important things in life.	1	2	3	4	5	
I get help when I’m sick in bed.	1	2	3	4	5	

SECTION F: SOCIAL CONSTRAINTS—Survivors Only

Sometimes, even when people have good intentions, they may say or do things that upset you. Think about the last two weeks and indicate how often the most important person in your life did the following things. Use the scale that ranges from: 1=Never, 2=Rarely, 3=Sometimes, 4=Often. Please circle only one response for each question.

	Never	Rarely	Sometimes	Often
How often did you feel that you had to keep your feelings about your breast cancer to yourself, because they made the most important person in your life feel uncomfortable?	1	2	3	4

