How often when you talked about your breast cancer, did the most important person in your life give you the idea that he/she didn't want to hear about your cancer?	1	2	3	4
How often did the most important person in your life let you down by not showing you as much love and concern as you would have liked?	1	2	3	4
How often has the most important person in your life really got on your nerves?	1	2	3	4

In the previous questions can you tell me who did you rate as the most important person in your life?

___ A friend ___ Spouse ___ Mother ___ Father ___ Sister ___ Other (Specify) _____

PRINCIPAL INVESTIGATOR (LAST, FIRST, MIDDLE): [name]

SECTION G: DYADIC COPING – Survivors and Caregivers

	Never true	Seldom true	Sometimes true	Often True	Always True
My family member is willing to listen to me when I just need to talk					
My family member gives me a great deal of affection and warmth.					
My family member ignores or makes light of my concerns.					
My family member supports me as I try to cope with the illness.					
When around my family member, I pretend things are going better than they really are.					
My family member and I work as a team to manage the effects of the illness.					
My family member gives me positive feedback for my attempts to cope with the illness.					

PRINCIPAL INVESTIGATOR (LAST, FIRST, MIDDLE): [name]

Social Health

	Excellent	Very Good	Good	Fair	Poor
In general, would you say your health is:					

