The next few questions are about your thoughts and opinions about learning about cancer and its impact. I will read you the question and then the answer choices.

Learning about cancer and its impact is important for both my spouse and I.	Strongly Disagree	Disagree	Uncertain	Agree	Strongly Agree
Whether my [name of other person's role: spouse/ partner/ sister/ mom/daughter] learns about cancer and its impact could affect my future too.	Strongly Disagree	Disagree	Uncertain	Agree	Strongly Agree
If my [spouse/ partner/ sister/ mom/ daughter] plans to learn about cancer and its impact, I would say that is a good idea.	Strongly Disagree	Disagree	Uncertain	Agree	Strongly Agree
I can think of reasons learning about cancer and its impact is important to my [spouse/ partner/ sister/ mom/ daughter]	Strongly Disagree	Disagree	Uncertain	Agree	Strongly Agree

PRINCIPAL INVESTIGATOR (LAST, FIRST, MIDDLE): [name]

SECTION P: COMMUNICATION SELF-EFFICACY—Survivors and Caregivers

The following questions ask about your communications with your caregiver. On a scale of 1 to 10, 1 meaning “not at all confident” and 9 meaning “totally confident”, please tell me how confident you are that you can talk with your caregiver about the following things.

SURVIVORS: I am confident in my ability to...	How confident are you? 1 to 10	N/A
Talk with my caregiver about my cancer		
Talk with my caregiver about changes in my body due to treatment		
Talk with my caregiver (if a spouse or partner) about our sexual relationship		
Talk with my caregiver about my fears		
Talk with my caregiver about future appointments with my doctor		
Talk with my caregiver about getting a will or other end of life documents		
Talk with other members of my family about my breast cancer		
Talk with my caregiver to ask for extra help or support		

CAREGIVERS: I am confident in my ability to...	How confident are you? 1 to 10	N/A
Talk with the survivor about her cancer		
Talk with the survivor caregiver about changes in her body due to treatment		
Talk with the survivor (if a spouse or partner) about our sexual relationship		
Talk with the survivor about my own fears		
Talk with the survivor about future appointments with her doctors		
Talk with the survivor about getting a will or other end of life documents		
Talk with other members of my family about the survivor’s breast cancer		
Talk with other members of my family to ask for extra help or support in providing care to the survivor.		

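### The draft dyadic scales do not consistently ask about the enrolled partner, so survivor-caregiver communication may be rated on someone outside the randomised pair

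*Combined protocol and SAP*

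**What the plan says.** **The outcome.** Section C.1, Choice of Outcomes: "Secondary outcomes include communication (survivor-caregiver and survivor-provider), satisfaction with cancer care and adherence to guideline concurrent follow-up care". The Secondary Outcomes paragraph adds: "Communication with caregivers will be measured through several dyadic-based measures". It does not name those measures. The Dyadic Factors paragraph that follows lists dyadic support, dyadic perspective and social constraints, and says of the dyadic support scale that it "assesses the perceived support received by each member of the patient-caregiver dyad".

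**The enrolled partner.** Section C.2, Inclusion/Exclusion Criteria: "Caregivers can be any adult identified by the survivor as providing care (e.g., spouse, adult child, friend". Only one caregiver is recruited per survivor.

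**The script (Appendix D).**
- Section F, social constraints, survivors only: "Think about the last two weeks and indicate how often the most important person in your life did the following things". It then asks: "In the previous questions can you tell me who did you rate as the most important person in your life". The response options are friend, spouse, mother, father, sister and other.
- Section G, dyadic coping, both members: the first item is "My family member is willing to listen to me when I just need to talk". All seven items use the same term, and no introduction says which person is meant.
- Section O, Thinking Beyond Oneself, both members: item 1 is "Learning about cancer and its impact is important for both my spouse and I". Items 2 to 4 carry a placeholder for the other person's role, listing spouse, partner, sister, mom and daughter.
- Section P, communication self-efficacy, names the caregiver or the survivor as the other party.

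**The concern.** The trial randomises a pair, and the outcome concerns communication within that pair. A scale that lets the respondent rate someone else measures a different relationship for part of the sample. If PCI changes the enrolled relationship more than others, those answers carry less of the treatment effect and pull the between-arm difference towards zero. If the rated person changes between baseline, T1 and T2, the score can move although neither relationship has. A null result on this outcome would then be hard to read: it could mean that PCI does not help, or that too many answers were about someone outside the trial. This cannot be repaired after data collection, because Section F records only a relationship type, and Sections G and O record nothing about who was rated.

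**Working it through.** There is no figure to reproduce. The Data Analyses section gives no aim, model or power statement for survivor-caregiver communication. The check is therefore a comparison of texts, followed by a dilution formula with assumed inputs.

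**1. From outcome to scales.** The outcome is to be measured by several dyadic measures, and the next paragraph but one lists three dyadic factors. Reading those three as the outcome's scales is natural, but it is an inference: Table 4 lists Communication (Caregiver) among the secondary outcomes and the three scales under a separate heading. Taking Section G as the dyadic support scale is also a reading, because it is headed dyadic coping and has seven items where the protocol describes five.

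**2. Scale by scale, against the enrolled partner.**

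| Section | Person rated | Fit with the enrolled partner |
|---|---|---|
| F (survivors) | Whoever the survivor holds most important | Left open. The follow-up item records a type of relationship: an answer of friend does not show whether she is the enrolled friend, and an adult child falls under other. |
| G (both) | An unspecified family member | Does not fit a friend dyad. Ambiguous where there are several relatives. |
| O, item 1 (both) | Spouse | Fits spouse dyads only. |
| O, items 2-4 (both) | The other person's role | Tied to the partner, but the printed list lacks friend and son. |
| P (both) | Caregiver or survivor | Tied to the partner, but the protocol classes this scale as a mediator. |

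**3. Any instruction that closes the gap?** Section Q carries a note that its items will be adapted. Sections F and G carry no such note, and Section O has only the placeholder in items 2 to 4. No text tells the interviewer to substitute the enrolled partner, and no planned analysis uses the Section F follow-up item.

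**4. Direction and possible range.** Let q be the share of respondents who rate someone else, and r the PCI effect on that other relationship as a fraction of its effect on the enrolled pair. Then

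observed effect = true effect × [(1 − q) + q·r].

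The documents give neither q nor r; both are assumptions.

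| q | r = 0 (no carry-over) | r = 0.5 | r = 1 (full carry-over) |
|---|---|---|---|
| 10% | 0.90 | 0.95 | 1.00 |
| 20% | 0.80 | 0.90 | 1.00 |
| 30% | 0.70 | 0.85 | 1.00 |
| 40% | 0.60 | 0.80 | 1.00 |

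For example, q = 20% and r = 0.5 give 0.80 + 0.20 × 0.5 = 0.90. The column r = 0 is the worst case when the effect on others is not negative. One q for all scales is also a simplification, since F is for survivors only and O is mostly tailored.

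**The case against.** Several points on the other side have force.

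- **Overlap may be large.** The caregiver is a primary support person chosen by the survivor, so she will often also be the most important person. The Section F follow-up shows that the rated relationship varies between women; it does not show that it differs from the enrolled one. This stands, and is why q cannot be guessed.
- **PCI teaches communication more widely.** Topic 4 in Table 3 covers family, friends and providers. The sample survivor session in Appendix A deals with children, other relatives, friends and partners, and its role-play concerns a family member. This stands: zero effect on other relationships is an extreme assumption.
- **A change of rated person occurs in both arms.** This stands: unless the arms differ in how often it happens, it adds noise to the comparison and not bias.
- **The interview is a draft, and the timeline schedules refinement of the surveys.** True, but nothing indicates that this wording is due for change.

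A reader might infer two stronger conclusions that the documents do not support. The first is that a survivor enrolled with her sister would rate her husband throughout. In Section O items 2 to 4 she would rate her sister, who is on the role list; in Section G a sister is a family member; in Section F the choice is open. Only Section O item 1 points to a spouse, and it asks about learning about cancer, not about how two people talk. The second is a stated loss of power. With 50 per arm, two-sided 0.05 and a 0.6 SD effect, power is 84.4%; at 0.6 × 0.8 = 0.48 SD it is 66%, and at 0.6 × 0.6 = 0.36 SD it is 43%. But the 0.6 SD and 84% belong to the PROMIS outcome in Aim 1. Communication has no planned power from which to fall, and these figures also require r = 0.

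**Conclusion.** The point holds as a defect of wording in secondary or dyadic measures. Section F leaves the rated person open, Section G gives no usable referent for friend dyads, and Section O item 1 and its role list do not cover the caregivers who may enrol. The likely result is noisier scores and a diluted difference between arms. The amount cannot be stated: it depends on the unknown share rating someone else and on how far PCI carries over to other relationships. It also rests on reading the dyadic factors as the measures of the communication outcome. If that reading is wrong, the scales still need the edit as dyadic measures, and the outcome then has no named instrument. The documents do not show that the outcome is measured on the wrong person in general. The primary PROMIS outcome is unaffected. The change should be made because it is cheap before recruitment and impossible afterwards.

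**What to change.** At baseline, T1 and T2, have the interviewer insert the enrolled partner's name or role in every item of Sections F, G and O, with friend and son added to the roles. Section P already anchors its items in this way. Keep the Section F follow-up item as a check, and add to it whether the person rated is the enrolled caregiver, so that mismatches can be counted. In the written analysis plan, state which of these scales form the Communication (Caregiver) outcome.

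The cost is a script edit to a draft interview, with one added field in Section F and no new scale items. The one downside is a slight departure from the Social Constraints wording that the team has used in Spanish with good internal consistency, so comparison with those data becomes a little less direct.
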